#### 10.3 TERMINATION CRITERIA

The study could be technically stopped as soon as 4 CRs are documented, but, in that case, accrual of a minimum of 12 patients is recommended to further document safety, pharmacologic endpoints and biomarkers.

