### Statistical methods

Up to 24 patients will be enrolled in the dose escalation phase Ib of the study (3 to 6 patients at each of the 4 dose levels).

After the completion of the part 1, dose escalation phase lb, up to 27 evaluable patients will be treated with IPH2201, as part of the phase IIa of the study, at the dosage recommended at the end of the first dose level. The 3 to 6 patients enrolled during the part 1 of the study, at the dosage recommended for the phase 2 part, may be included in the group of patients used for the assessment of efficacy, thereby reducing the sample size in part 2 from 24 to 21 patients.

Primary efficacy endpoint: complete response rate based on IWCLL criteria.

The significance level (alpha risk) is set at 0.05 and power at 80%. The one-sided null hypothesis is specified as  $H_0$ : p = 0.05 and the alternative  $H_1$ : p = 0.20, p the probability to achieve a CR.

Further investigation is deemed warranted if  $\geq 4$  patients achieve a CR by the end of the study ( $\geq 4/27$ ).

The study could be technically stopped as soon as 4 CRs are documented, but, in that case, accrual of a minimum of 12 patients is recommended to further document safety, pharmacologic endpoints and biomarkers.

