#### 10.2 SAMPLE SIZE

36 to 48 patients will be enrolled in this clinical study:

Up to 24 patients (3 to 6 patients at each dose level) will be enrolled in the dose-escalation phase Ib Up to 24 patients in the phase IIa

The 3 to 6 patients treated during the phase Ib with the phase IIa recommended dose will be included in the efficacy analysis set of the phase IIa part.

If 6 patients (3+3 for safety reasons) are treated during the phase Ib with the phase IIa recommended dose, a maximum of 21 patients will be included in the phase IIa

If 24 patients were enrolled in the phase Ib of the trial (including 6 at the recommended dose of the phase IIa, no more than 21 patients would need to be enrolled in the phase IIa; Which means than the total number of patients will never exceed 45 (24+21)

Primary efficacy endpoint: CR rate based on IWCLL criteria

The significance level (alpha risk) is set at 0.05 and power of at least 80%. The one-sided null hypothesis is specified as H0: p = 0.05 and the alternative H1: p= 0.20, p the probability to achieve a CR

Further investigation is deemed warranted if  $\geq$  4 patients achieve a CR by the end of the study ( $\geq$  4/27).

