3.3.2 Phase IIa

The design chosen for the calculation of the sample size is the one-stage Fleming design [2]. The hypotheses are α =0.05 one sided, power of 0.80. The one-sided null hypothesis is specified as H0: p =0.05 and the alternative H1: p= 0.20, p is the probability to achieve a CR. The sample size needed is 27 patients and the trial will be considered as positive if at least 4 CR are observed. The trial will be considered as negative if 3 CR or fewer are observed.

As the 3 to 6 patients treated during the phase Ib with the phase IIa recommended dose will be included in the efficacy analysis set of the phase IIa part, this means that 21 to 24 new patients will be enrolled in the phase IIa. This also means than the total number of patients will never exceed 45 (24+21).

4. General Analysis Definitions

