8.1 Rate of complete remission

In both phases, the rate of complete remission is assessed 52 weeks after the initiation of combined treatment

The rate of complete remission (CR) will be calculated in the main endpoint population (see §4.2.2). Within this population, the CR rate will be computed as the number of patients with a confirmed complete remission at W52 divided by the total number of patients in the main endpoint population.

The rate of complete remission with 95% confidence interval will be summarized overall and in the subgroup treated at the RP2D.

In order to claim a CR, the CR must be confirmed. In order to have a confirmed CR (cCR), the CR must be confirmed by a scan and a bone marrow assessment assessed at least 2 months after the first occurrence of CR.

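### The protocol permits a stop at the 4th CR, while the SAP analyses a fixed n of 27 and leaves the data cutoff open, so the reported CR rate could be biased upward on average

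*Protocol*

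**What the plan says.** Protocol 10.3, repeated in the synopsis under Statistical methods, contains an optional early stop for success: "The study could be technically stopped as soon as 4 CRs are documented". It adds that in that case "accrual of a minimum of 12 patients is recommended to further document safety". The 12 is therefore a recommendation, not a floor.

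SAP 3.3.2 describes something else: "The design chosen for the calculation of the sample size is the one-stage Fleming design", with the rule "The sample size needed is 27 patients and the trial will be considered as positive if at least 4 CR are observed". It mentions no early stop. The SAP states that it is based on protocol version 5.0, which contains the clause, but it neither adopts the option nor sets it aside.

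SAP 8.1 takes the confirmed CRs at W52 "divided by the total number of patients in the main endpoint population" and adds a 95% confidence interval. It names no interval method and makes no allowance for stopping. SAP 4.2.2 limits that population to patients whose first dose was at least 52 weeks before the data cutoff, and it also removes patients who left monalizumab for progression within 8 weeks. It does not say how the cutoff date is chosen. Protocol 10.1, by contrast, puts all analyses on all treated patients.

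**The concern.** If observation ends because the 4th CR has arrived, the sample size depends on the outcome. A run of early CRs closes the trial at a small denominator, while a slow start lets it run on to 27. Averaged over such trials, CRs divided by patients exceeds the true rate.

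There are two routes to this. Accrual could be halted at the 4th CR. Or accrual could be complete but the data cutoff set when the 4th CR is documented; SAP 4.2.2 then drops treated patients with less than 52 weeks since first dose. The second route needs no change in enrolment, and nothing in the SAP rules it out.

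At stake is the phase IIa primary estimate. The trial has no concurrent control, so this number would be set against the 5% and 20% reference rates and carried into planning of any further trial.

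**Working it through.** **1. The plan's own design.** SAP 3.3.2 gives "The hypotheses are α =0.05 one sided, power of 0.80" and "The one-sided null hypothesis is specified as H0: p =0.05 and the alternative H1: p= 0.20". With X the number of CRs in 27 patients, exact binomial:
- At p = 0.05: P(X ≥ 4) = 1 − (0.25034 + 0.35575 + 0.24341 + 0.10676) = 0.0437.
- At p = 0.20: P(X ≥ 4) = 1 − (0.00242 + 0.01632 + 0.05304 + 0.11050) = 0.8177.
- With 26 patients and the same rule, power is 0.7932. So 27 is the smallest n that meets both targets, and the stated design is reproduced.

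**2. Effect of the stop on the decision.** A trial that reaches 4 CRs before patient 27 would also have at least 4 at patient 27. Success is the same event with or without the stop, so 0.0437 and 0.8177 stand.

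**3. Effect on the estimate.** Assumptions: CRs become known in enrolment order; from patient 12 on, observation ends at the first n with at least 4 CRs; otherwise it runs to 27. All paths were enumerated exactly, and the mean reported rate is Σ P(end at n with k CRs) × k/n.

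| True rate | Mean rate, all trials | Expected n | P(end before 27) | Mean rate if ended before 27 | Mean rate if successful, with stop | Mean rate if successful, fixed 27 |
|---|---|---|---|---|---|---|
| 5% | 5.2% | 26.8 | 3.9% | 20.2% | 19.6% | 15.8% |
| 10% | 11.1% | 25.1 | 25.9% | 21.7% | 21.1% | 17.4% |
| 15% | 17.1% | 22.2 | 56.1% | 23.6% | 23.1% | 19.5% |
| 20% | 22.7% | 19.1 | 79.3% | 26.1% | 25.8% | 22.4% |
| 30% | 32.3% | 14.7 | 97.4% | 32.9% | 32.7% | 30.4% |

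If the recommended 12 is not observed, the mean at a true 20% is 24.1% over all trials and 27.8% given an early end.

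**4. Interval.** Under the same rule a Clopper-Pearson 95% interval keeps coverage above 95% at all five rates; the lowest value is 96.2%, at a true 20%.

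**5. Calendar.** Protocol 3.4 plans up to 45 patients in about 18 months. Assuming uniform accrual, 45/18 = 2.5 per month, so the 21 to 24 phase IIa patients enrol in 21/2.5 = 8.4 to 24/2.5 = 9.6 months. That is before the first of them reaches W52. Marrow confirmation comes at least 2 months after CR criteria are met. The phase Ib patients at the recommended dose start sooner, but there are at most 6. At a true 20%, the chance of 4 or more CRs among 6 is 15(0.2⁴)(0.8²) + 6(0.2⁵)(0.8) + 0.2⁶ = 0.01536 + 0.00154 + 0.00006 = 0.017.

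**6. Estimate that allows for the stop.** If observation truly ends at patient n > 12 with the 4th CR, the minimum-variance unbiased estimate is the share of admissible paths in which the first patient responds: C(n−2, 2)/C(n−1, 3) = 3/(n−1). For n = 20 this is 153/969 = 15.8%, against a raw 4/20 = 20.0%. An end at exactly 12 keeps k/12, and a trial reaching 27 with 3 or fewer CRs keeps k/27. In the enumeration this estimator averages to the true rate at all five rates in the table.

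**The case against.** The strongest reply is that the modelled sequence does not fit the trial's calendar. Reading CRs one patient at a time and halting accrual at the 4th would require four CRs to be documented within about 9 months of phase IIa opening. The primary reading is at W52, and Protocol 7.1 even requires CR criteria to be assessed at least 2 months after IPH2201 is discontinued. The protocol's own background (1.1.5.1) gives a 12-month CR rate on ibrutinib alone of only 6% in untreated patients. This stands. An expected n of 19.1 is an output of the model, not an enrolment forecast. It is not absolute, because the clause speaks of CRs documented rather than CRs at W52, and disease is assessed monthly.

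Second, neither document ties the cutoff to the 4th CR, and the 52-week condition has a sound purpose: it stops patients who have not reached the endpoint from counting as failures. That also stands. The point is that the SAP leaves the cutoff open beside a protocol clause that makes the 4th CR a natural moment to stop.

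Third, the clause is permissive, Protocol 10.1 calls the analyses descriptive, and the decision depends only on the count of CRs. All true; this limits the point to the estimate.

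A reader might infer that the option inflates type I error. It does not (step 2). A reader might also infer that any early stop reports too high a rate. Under the model that is so at true rates of 5% to 15%, but at 20% only 69% of early stops exceed the truth. Part of the excess among successful trials is also present with fixed n (22.4% at a true 20%).

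**Conclusion.** The point holds as a gap between the protocol and the SAP that affects the primary estimate only. If the option were used, or the cutoff set at the 4th CR, the raw CR rate would be too high on average: by 2.7 percentage points at a true 20%, 2.1 at 15% and 1.1 at 10%. Given success at 20%, it averages 25.8% against 22.4% with fixed n. The test, the power, the go/no-go rule and the coverage of an exact interval are not affected.

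These sizes rest on CRs being known in enrolment order and on observation ending at the 4th. For the cutoff route they are a guide only. If confirmation takes 2 months, about 2 × 2.5 = 5 further patients would pass 52 weeks before the cutoff and dilute the effect. The realistic exposure is the cutoff and denominator rather than truncated enrolment; the calendar argument assumes uniform accrual at the planned pace. The documents do not support the stronger statement that an inflated rate will be reported. They support saying that nothing in the SAP prevents it.

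**What to change.** Either of two changes is enough.

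- **Delete the early-stop clause** from Protocol 10.3 and the synopsis. This is a protocol amendment, not just SAP wording.
- **Keep the clause and add a sentence to SAP 4.2.2 and 8.1:** if accrual stops early, the data cutoff is set at least 52 weeks after the first dose of the last patient dosed, so that every patient dosed by the stop and otherwise in the main endpoint population is followed to the primary time point and counted. This removes most of the bias.

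The estimate 3/(n−1) should not be the primary figure under the second option. It is unbiased only when observation ends at the patient with the 4th CR, and it does not apply once later patients are followed and may add CRs. It can serve as a sensitivity figure if observation really did end there at n > 12.

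If accrual has already reached its target, one sentence saying that the option was not used and that the cutoff covers all dosed patients closes the matter. The planned dates (first visit November 2015, about 18 months of recruitment, SAP 2.0 approved March 2019) suggest that this may be known.

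Cost: no added patients and no change to the decision rule. The downside is small: a later readout and possibly a lower headline rate after an early stop.

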#### 10.4 DEVIATIONS

Any deviation from the initial analysis plan will be described in the Clinical Study Report.

#### CONFIDENTIAL

Release date: Edition number

GED version

# 10.5 SELECTION OF SUBJECTS

Evaluable patients: all patients who received at least 1 administration of IPH2201 will be evaluable for efficacy and safety. Patients who do not receive at least 1 administration of IPH2201 will be documented in the study report. These patients will be replaced to reach a total of 27 evaluable patients. In addition, in the two phases of the trial (Ib and IIa), patients will be replaced in case of treatment discontinuation of IPH2201 due to disease progression before the end of 8 weeks of treatment.

#### 10.6 Access to Data

The investigator will make all study-related source data and documents available to the Monitor or a quality assurance auditor mandated by the sponsor, or to domestic or foreign regulatory inspectors, after appropriate notification.

#### 10.7 Source Data and Documents

Source data are defined as all information available in the original source documents or certified copies of the source document of any clinical findings, observations, or other activities that are necessary for the reconstruction and evaluation of the study.

For each patient included, the investigator will indicate in the source documents that the patient participates in this study, and will record the appropriate information. This will include (non-exhaustive list): patient name, date of birth, sex, medical history, information that the patient is included in the study, visit dates, product administration, primary evaluation criteria, nature of AEs with date of start and related treatment.

Source documents will be preserved for the maximum period of time requested by local recommendation or ICH, whichever occurs last.

Release date: Edition number

GED version

# 11 QUALITY CONTROL AND QUALITY ASSURANCE

#### 11.1 Source Data and Documents

In addition to the initial visit for site-initiation, the monitor will contact and visit the investigator periodically to evaluate the study progress and the compliance of the study site with GCP, regulations and the study protocol as well as to verify and collect data reported in the EDC System. The investigator as well as any study staff member will cooperate with the monitor to ensure that any problem that may be identified is resolved.

For this study, the average frequency of the monitoring visits is intended to be approximately 6 weeks when patients are not yet in the follow-up period, with the first visit occurring as soon as possible after the first patient inclusion. Intervals may be adjusted according to patient enrolment, protocol changes or site performance.

#### 11.2 Periodic Monitoring

Innate Pharma will provide an EDC system to allow data entry by site users (Investigator and Investigator's authorized staff). EDC system development will be delegated to Each member of the site will be assigned a username, a personal login and a password to enter into the EDC system. Each login uniquely identifies the user. Appropriate permissions for system access will be set-up according to the user's role. The access to the system will be granted once the user's training has been completed and documented.

The eCRF will be set-up in a way that facilitates navigation and data entry by the site personnel.

All study documentation will be securely stored and maintained in an electronic trial master file (eTMF).

#### 11.3 Data Management

Data will be entered into the EDC system on an ongoing basis, ensuring all relevant items are completed, there is no missing data and that all data entered are consistent with the source documentation.

Data will be entered according to the data entry instructions provided.

The investigator will confirm that the information is complete and accurate by signing the electronic forms.

#### 11.3.1 Data Entry

The data will be electronically verified through use of automatic checks during data entry, SAS programmed edit checks to check complex conditions (if any) and data monitoring.

Data correction will be made by site users.

An audit trail will identify the person entering/correcting the data, date and time of data entry and reason for correction.

#### CONFIDENTIAL

Release date: Edition number

GED version

#### 11.3.2 Data Review

Real-time online reports will be available in the EDC system.

Sponsor, Monitors and Data managers will have the possibility to generate manual queries in the EDC system.

Monitors are responsible for source data verification. As soon as the data have been reviewed by the monitor, they should be signed by the monitor in order to allow the investigator to sign the data.

The investigator signature is equal to a legal signature. As soon as the data have been signed by the investigator, the data are frozen. The data can no longer be changed unless a request of unfreeze is sent to the data manager.

# 11.3.3 Data Coding

AEs will be reported and graded according to the NCI-CTCAE version 4.03 of 14th June 2010 by the investigator. AEs will be coded according to the MedDRA dictionary.

# 11.3.4 Study

Database will be recorded on CD-ROM.

At the end of the trial, Patient eCRF data will be provided on CD to the Investigator site in an electronic readable format for archiving.

#### 11.3.6 SAE data reconciliation

The CRO in charge of data management and CRO in charge of Pharmacovigilance will collaborate in the performance of the safety data reconciliation.

#### 11.3.7 Data Freezing

Before database lock, all queries must be resolved and coding must be validated by the Sponsor. Reconciliation of SAEs between the clinical database and the Pharmacovigilance database also has to be completed. The data will be extracted from the database into the data files for statistical analysis.

# 11.4 AUDIT AND INSPECTION

The main purposes of an audit or inspection are to confirm that the rights and well-being of the patients have been adequately protected, and that all data relevant for the evaluation of the study drug have been processed and reported in compliance with ICH GCP and applicable regulatory requirements.

Release date: Edition number

GED version

# 12 ETHICS

#### 12.1 ETHICAL CONDITIONS

This study will be performed in accordance with the principles stated in the Declaration of Helsinki and subsequent amendments and in accordance with the Guidance on GCP (CPMP/ICH/135/95).

# 12.2 INDEPENDENT ETHICS COMMITTEE/INSTITUTIONAL REVIEW BOARD (IEC/IRB) APPROVAL

The investigator is responsible for ensuring that this protocol and the consent form have been reviewed and approved by a relevant IEC/IRB prior to the start of the study. The IEC/IRB shall be appropriately constituted and perform its functions in accordance with the Food and Drug Administration, ICH/GCP and local requirements as applicable.

In addition, the IEC/IRB shall approve all protocol amendments (except for logistical or administrative changes), written informed consent documents and document updates, patient recruitment procedures (e.g. advertisements), written information to be provided to patients, the Investigator's Brochure, available safety information, information about payment and compensation available to patients, the Investigator's *curriculum vitae* and/or other evidence of qualifications and any other documents requested by the IEC/IRB and Regulatory CA as applicable.

The investigator is responsible for keeping the IEC/IRB informed of the progress of the study and of any changes made to the protocol as deemed appropriate, but in any case at least once a year. The investigator must also keep the IEC/IRB informed of any serious and significant AEs.

#### 12.3 Patient Information and Consent

Information providing the common features of the research must be given to patients themselves. Restraints and risks must be explained, as well as the right to refuse or discontinue their participation in the study at any stage, without further affecting the relationship with the investigator and/or their future care.

This written information and consent form will be given to the patient with an oral explanation before the patient enters the study and it will be agreed and signed by the patient. The investigator is responsible for ensuring that written informed consent is obtained for all patients.

For a patient who is legally incompetent, or physically or mentally incapable of giving consent, the investigator must obtain informed consent from the patient's legally authorized representative in accordance with applicable laws.

Two original copies of the information and consent document will be produced; one copy will be kept by the investigator and the other copy will be given to the patient.

If any information becomes available during the study that may be relevant to the patient's willingness to keep on participating in the study, an updated informed consent must be submitted to the patient to confirm his/her agreement to continue participating.

#### CONFIDENTIAL

Release date: Edition number

GED version

# 12.4 CONFIDENTIALITY

In compliance with United States federal regulations, Innate Pharma requires the Investigator(s) to permit Innate Pharma's representatives and, when necessary, representatives of the FDA or other regulatory authorities to review and/or copy any medical records relevant to the study in accordance with local laws.

The present materials (protocol, CRF, investigator's brochure) contain confidential information. The investigator agrees to hold such information in confidence, and not to disclose it to others (except where required by applicable law) except as may otherwise be agreed to in writing with the sponsor.

#### 12.5 Data Handling and Record Keeping

The investigator will be kept informed of the methods used for the relevant ratings and completion of CRFs, and of important information that relates to the safe use of the study drug(s) as the study proceeds.

The site's staff, e.g. residents, nurses, laboratory technicians and any other personnel providing care to the study patients or handling biological specimen will be informed of the characteristics of the study drug and receive safety instructions.

#### 12.6 Investigators Information

The investigator will be kept informed of the methods used for the relevant ratings and completion of CRFs, and of important information that relates to the safe use of the study drug(s) as the study proceeds.

The site's staff, e.g. residents, nurses, laboratory technicians and any other personnel providing care to the study patients or handling biological specimen will be informed of the characteristics of the study drug and receive safety instructions.

